6.1.5. Dose Modifications

Dose modifications are discouraged. However, if a patient develops an SAE that the Investigator believes may be mitigated by a dose modification, the Medical Monitor should be contacted to discuss the possibility of a dose modification.

6.1.6. Compliance

Administration of CPX-POM will be performed by site personnel. Compliance will be assessed by inspection of drug accountability records at the study site.

6.1.7. Accountability

The investigator or designee (i.e., pharmacist) is responsible for ensuring adequate accountability of all used and unused investigational medicinal product, placebos, and comparators. This includes acknowledgment of receipt of each shipment of investigational product (quantity and condition), patient dispensing records, and returned or destroyed study product. Dispensing records will document quantities received from CicloMed and quantities administered to patients, including lot number, date dispensed/administered, patient identifier number, and the initials of the person dispensing/administering the medication.

At study initiation, the monitor will evaluate the site's standard operating procedure for investigational medicinal product disposal/destruction in order to ensure that it complies with CicloMed requirements. Drug may be returned or destroyed on an ongoing basis during the study, if appropriate. At the end of the study, following final drug inventory reconciliation by the monitor, the study site will dispose of and/or destroy all unused investigational medicinal product supplies, including empty containers, according to these procedures. If the site cannot meet CicloMed's requirements for disposal, arrangements will be made between the site and CicloMed or its representative for destruction or return of unused investigational medicinal product supplies.

All drug supplies and associated documentation will be periodically reviewed and verified by the study monitor over the course of the study.

Further guidance and information for the final disposition of unused investigational product is provided in the Study Procedures Manual.

6.2. Prior and Concomitant Medications

Medications taken within 30 days before baseline (Study Visit 2) must be recorded as prior medications.

Prohibited concomitant medications include any anti-cancer agents, steroids, any iron replacement therapy, warfarin, or any drug known to have significant nephrotoxicity. A minimum of 10 days between termination of the prohibited concomitant medications or a duration of five elimination half-lives will be required prior to administration of IV CPX-POM to eligible patients. Concomitant radiation therapy is also prohibited.

Note that anti-emetics such as ondansetron or granisetron are allowed if used with caution and attention to the approved labelling.

All concomitant medications will be recorded from the time of Screening up to the time of TURBT. Routine medications associated with the cystectomy procedure do not need to be recorded. Starting at the time of TURBT, only medications associated with an AE related to CPX-POM treatment need to be recorded.

7. DISCONTINUATION OF STUDY INTERVENTION AND PATIENT DISCONTINUATION/WITHDRAWAL

7.1. Discontinuation of Study Treatment

In the event of discontinuation of CPX-POM, every effort should be made to complete the assessments that are scheduled for the Follow-up/Early Termination visit. See the Schedule of Assessments ([Table 1](#)) for data to be collected at the time of early termination.

7.2. Patient Discontinuation/Withdrawal from the Study

A patient may withdraw from the study at any time at his/her own request, or may be withdrawn at any time at the discretion of the investigator for safety, behavioral, compliance, or administrative reasons. The patient will be withdrawn before any CPX-POM treatment is administered if the in-office cystoscopy fails to confirm bladder tumor.

If the patient withdraws consent for disclosure of future information, the Sponsor may retain and continue to use any data collected before such a withdrawal of consent.

If a patient withdraws from the study, he/she may request destruction of any samples taken and not tested, and the investigator must document this in the site study records.

If a patient withdraws prematurely from the trial for any reason, study staff should make every effort to complete the full set of evaluations scheduled for the Follow-up/Early Termination visit. See the Schedule of Assessments ([Table 1](#)) for data to be collected at the time of early termination.

7.3. Lost to Follow Up

A patient will be considered lost to follow-up if he or she repeatedly fails to return for scheduled visits and is unable to be contacted by the study site.

The following actions must be taken if a patient fails to return to the clinic for a required study visit:

- The site must attempt to contact the patient and reschedule the missed visit as soon as possible and counsel the patient on the importance of maintaining the assigned visit schedule and ascertain whether or not the patient wishes to and/or should continue in the study.
- Before a patient is deemed lost to follow up, the investigator or designee must make every effort to regain contact with the patient (where possible, 3 telephone calls and, if

necessary, a certified letter to the patient's last known mailing address or local equivalent methods). These contact attempts should be documented in the patient's medical record.

- Should the patient continue to be unreachable, he/she will be considered to have withdrawn from the study.

8. STUDY ASSESSMENTS

8.1. Safety Assessments

8.1.1. Adverse Events and Serious Adverse Events

8.1.1.1. Definitions

Adverse Event

An AE is any untoward medical occurrence in a clinical investigation subject administered a medicinal product and which does not necessarily have a causal relationship with this treatment. An AE can therefore be any unfavorable and unintended sign, symptom, or disease temporally associated with the use of a medicinal product, whether or not considered related to the medicinal product.

AEs also include the following:

- Pre- or post-treatment complications that occur as a result of protocol mandated procedure (e.g., such as venipuncture, biopsy) during or after Screening (before the administration of study investigational medicinal product).
- Any pre-existing condition that increases in severity, or changes in nature during or as a consequence of the study investigational medicinal product phase of a human clinical trial, will also be considered an AE.
- Complications and termination of pregnancy (see Section [8.1.2](#) for additional information)
- All AEs that occur from the study screening visit onwards and throughout the duration of the study, including the follow-up off study medication period should be recorded as an AE.

An AE does not include the following:

- Medical or surgical procedures (e.g., surgery, endoscopy, tooth extraction, transfusion) performed; the condition that leads to the procedure is an AE.
- Pre-existing diseases or conditions or laboratory abnormalities present or detected before the screening visit that do not worsen.
- If progression of underlying malignancy is clearly consistent with the suspected progression of the underlying cancer as defined by the Response Evaluation Criteria in Solid Tumors (RECIST) 1.1, or with clinical symptoms (clinical progression), it should not be reported as an AE/SAE. Similarly, hospitalization due exclusively to the progression of underlying malignancy should NOT be reported as an SAE.

- Situations where an untoward medical occurrence has not occurred (e.g., hospitalization for elective surgery, social and/or convenience admissions).
- Any medical condition or clinically significant laboratory abnormality with an onset date before the consent form is signed and not related to a protocol-associated procedure is not an AE. It is considered to be pre-existing and should be documented on the medical history case report form (CRF).
- Uncomplicated pregnancy.
- An induced elective abortion to terminate a pregnancy without medical reason.
- "Lack of efficacy" or "failure of expected pharmacological action" per se will not be reported as an AE or SAE. However, the signs, symptoms, and/or clinical sequelae resulting from lack of efficacy may be reported as AE or SAE if they fulfill the definition of an AE or SAE.

Serious Adverse Event

If an event is not an AE per definition above, then it cannot be an SAE even if serious conditions are met (e.g., hospitalization for signs/symptoms of the disease under study, death due to progression of disease).

An **SAE** is defined as any untoward medical occurrence that, at any dose:

- Results in death
- Is life-threatening. The term 'life-threatening' in the definition of 'serious' refers to an event in which the patient was at risk of death at the time of the event. It does not refer to an event, which hypothetically might have caused death, if it were more severe.
- Requires inpatient hospitalization or prolongation of existing hospitalization. In general, hospitalization signifies that the patient has been detained (usually involving at least an overnight stay) at the hospital or emergency ward for observation and/or treatment that would not have been appropriate in the physician's office or outpatient setting. Complications that occur during hospitalization are AEs. If a complication prolongs hospitalization or fulfills any other serious criteria, the event is serious. When in doubt as to whether "hospitalization" occurred or was necessary, the AE should be considered serious. Hospitalization for elective treatment of a pre-existing condition that did not worsen from baseline is not considered an AE.
- Results in persistent disability/incapacity. The term disability means a substantial disruption of a person's ability to conduct normal life functions. This definition is not intended to include experiences of relatively minor medical significance such as uncomplicated headache, nausea, vomiting, diarrhea, influenza, and accidental trauma (e.g., sprained ankle) which may interfere with or prevent everyday life functions but do not constitute a substantial disruption.

- Is a congenital anomaly/birth defect in the offspring of a subject who received investigational medicinal product.
- Other situations. Medical or scientific judgment should be exercised in deciding whether SAE reporting is appropriate in other situations such as important medical events that may not be immediately life-threatening or result in death or hospitalization but may jeopardize the patient or may require medical or surgical intervention to prevent one of the other outcomes listed in the above definition. These events should usually be considered serious. Examples of important medical events include invasive or malignant cancers, intensive treatment in an emergency room or at home for allergic bronchospasm, blood dyscrasias or convulsions that do not result in hospitalization, or development of drug dependency or drug abuse.

8.1.1.2. Time Period and Frequency for Collecting Adverse Event and Serious Adverse Event Information

All AEs and SAEs will be collected from the signing of the informed consent form (ICF) through the Follow-up visit (28 +/- 5 days after the last dose of study drug).

Medical occurrences that begin before the start of study intervention but after obtaining informed consent will be recorded on the Medical History/Current Medical Conditions section of the CRF not the AE section.

Investigators are not obligated to actively seek AE or SAE after conclusion of the study participation. However, if the investigator learns of any SAE, including a death, at any time after a patient has been discharged from the study, and he/she considers the event to be reasonably related to the study intervention or study participation, the investigator must promptly notify the Sponsor.

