3. Pre-treatment bladder tumor tissue sample will be obtained during in-office cystoscopy by cold cup biopsy within 4 weeks of TURBT. Post-treatment bladder tissue sample will be obtained at surgical resection (TURBT) on Day 5.
4. Hematology will include measurement of hemoglobin, hematocrit, platelets, RBC, reticulocytes, and WBC with differential.
5. Clinical chemistry will include measurement of potassium, sodium, chloride, glucose, BUN, creatinine, creatinine clearance, ALT, AST, GGT, alkaline phosphatase; indirect bilirubin, direct bilirubin, total bilirubin, total protein, albumin, calcium, bicarbonate, magnesium, phosphate, lipase, and amylase.
6. Urinalysis will include color, turbidity, pH, specific gravity, glucose, ketones, nitrites, bilirubin, urobilirubin, protein, RBCs, WBCs, epithelial cells, casts, crystals, and bacteria, and eGFR at Screening only.
7. A full physical examination will be conducted at Screening and at Visit 7/Follow-up. At each other study visit, patients will be assessed for continued dosing and any possible physical symptoms/toxicities and a physical examination may be performed, if indicated. Body weight should be measured at each study visit. Height should be measured at Screening.
8. Vital signs will be measured before any blood draws scheduled for the same time point. Vital signs will include blood pressure, respiratory rate, pulse, oxygen saturation, and temperature.
9. At Screening, 12-lead ECGs will be performed in triplicate, with each measurement separated by 2 minutes. The average of the 3 screening ECGs will be used to calculate QTc interval to determine study eligibility. Thereafter, single 12-lead ECGs will be performed for all patients prior to drug administration on Days 1 and 5 and at the Final Study visit.
10. All AEs and SAEs will be collected from the signing of the informed consent form through the time of TURBT. Starting at TURBT, only AEs related to CPX-POM treatment should be recorded; AEs related to the TURBT will not need to be recorded.
11. All concomitant medications will be recorded from the time of Screening up to the time of TURBT. Starting at TURBT, only medications associated with an AE related to CPX-POM treatment need to be recorded; routine medications and medications associated with the TURBT procedure do not need to be recorded.

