### **9.4 Adverse Events**

All adverse event summaries will be restricted to Treatment Emergent Adverse Events (TEAE), which are defined as those AEs that occurred after first CPX-POM dosing and those existing AEs that worsened during the study. This will not include AEs that are due to the operative TURBT procedure. If it cannot be determined whether the AE is treatment emergent due to incomplete or missing data, then it will be considered treatment emergent. Verbatim terms will be mapped to preferred terms and system organ classes using the Medical Dictionary for Regulatory Activities (MedDRA) (version 23.1).

Summaries that are displayed by system organ class and preferred terms will be ordered by descending order of incidence of system organ class and preferred term within each system organ class. The following summaries will be provided:

- Overall summary of AEs
- TEAEs by system organ class and preferred term
- TEAEs by system organ class, preferred term, and highest intensity
- Related TEAEs by system organ class and preferred term
- Serious TEAEs by system organ class and preferred term
- Serious Related TEAEs by system organ class and preferred term
- TEAEs leading to study discontinuation by system organ class and preferred term
- TEAEs resulting in death

Related events will be any event having the causality field marked as “Related” or missing on the Adverse Event eCRF page. Intensity (Grade) of AEs will be based on the NCI Common Terminology Criteria for Adverse Events (CTCAE) (5.0).

All AEs will be provided in a listing.

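### Protocol 8.1.1.2 sends events between consent and first dose to Medical History, although 8.1.1.1 and Table 1 make them AEs; biopsy complications and pre-dose serious events could be missing from the AE listing

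*Protocol*

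**What the plan says.** Protocol 8.1.1.2 gives two instructions in consecutive paragraphs. The first sets the collection window: "All AEs and SAEs will be collected from the signing of the informed consent form (ICF) through the Follow-up visit". The second deals with the time before dosing: "Medical occurrences that begin before the start of study intervention but after obtaining informed consent will be recorded" in a place it then names, namely that they "will be recorded on the Medical History/Current Medical Conditions section of the CRF not the AE section".

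Other places in the protocol agree with the first instruction:

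- Protocol 8.1.1.1 asks for an AE record for "All AEs that occur from the study screening visit onwards and throughout the duration of the study".
- The same section counts as AEs "Pre- or post-treatment complications that occur as a result of protocol mandated procedure (e.g., such as venipuncture, biopsy) during or after Screening", and adds in brackets that this means before study drug is given.
- The same section limits what belongs in Medical History: a condition or significant laboratory abnormality "with an onset date before the consent form is signed and not related to a protocol-associated procedure is not an AE".
- Table 1 marks AEs at the screening visit, and footnote 10 states: "All AEs and SAEs will be collected from the signing of the informed consent form through the time of TURBT".

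SAP 9.4 restricts the AE summaries to treatment-emergent events, which include "those existing AEs that worsened during the study", and also plans a listing of all AEs.

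**The concern.** A site cannot follow both rules for an event that starts after consent and before the first dose. The window is not empty of risk, because the cystoscopy and cold cup biopsy fall inside it. A complication of that biopsy is an AE under 8.1.1.1 and is kept off the AE page by 8.1.1.2.

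The choice of page matters because the protocol attaches its assessments to AEs and SAEs. Section 8.1.1.7 requires a grade for them, and 8.1.1.6 requires causality, including the relation to procedures such as biopsy. Nothing in the documents says that a Medical History entry receives either. Safety is the primary objective and there are about 12 patients, so by-patient listings carry much of the safety reporting. Two members of site staff could file the same event differently, and both could cite the protocol.

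**Working it through.** No sample size, power or alpha figure is involved. The check sets the rules side by side and follows each kind of event into the planned outputs.

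**Step 1. Where each rule puts an event**

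| Event | Protocol 8.1.1.1 and Table 1, footnote 10 | Protocol 8.1.1.2, second paragraph |
|---|---|---|
| Onset before consent, unrelated to a protocol procedure | Medical History | Not addressed |
| Biopsy or venipuncture complication after consent, before first dose | AE | Medical History, not AE |
| Other event after consent, before first dose | AE | Medical History, not AE |
| Serious event after consent, before first dose | Collected as an SAE | Medical History, no exemption |
| Onset after first dose | AE | Not affected |

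The rules collide in the three middle rows. The first sentence of 8.1.1.2 sides with the middle column, so the section also contradicts itself.

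**Step 2. Can the collision occur?** Yes. Protocol 8.1.3.1 places consent before the cystoscopy and biopsy, and Table 1 places both in the screening period, Day -28 to Day -1.

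**Step 3. What is lost if the site follows the Medical History sentence**

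- AE page: no record of the event.
- Grade (8.1.1.7) and relation to procedure (8.1.1.6): not assured, because both are specified for AEs and SAEs only.
- SAP 9.4 listing of all AEs: the event is absent.

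**Step 4. What is not lost**

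- AE summary tables: SAP 9.4 restricts them to treatment-emergent events, so an event that starts and ends before dosing enters none of them under either rule.
- Laboratory toxicity grades: SAP 9.5 derives them from laboratory values, not from AE records.
- The event itself: SAP 7.3 codes medical history in MedDRA, summarises it by system organ class and preferred term, and lists it.
- Notification: Protocol 8.1.1.4 and 8.1.1.5 require SAEs to reach the sponsor within 24 hours. The disputed sentence names a CRF section and does not withdraw that duty.

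**Step 5. Events that start before dosing and worsen afterwards.** Under 8.1.1.1, a pre-existing condition that becomes more severe in the treatment phase is an AE in its own right, and 8.1.1.7 requires a grade for it. If its onset is taken as the date of worsening, it is treatment-emergent under Protocol 9.5.1 and under the first limb of the SAP 9.4 definition. If its status cannot be determined because data are missing, SAP 9.4 counts it as treatment-emergent. What may be lost is the link to the earlier event and its starting grade. No planned AE table uses a starting grade, since SAP 9.4 tabulates highest intensity.

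**Step 6. Length of the window.** The synopsis gives up to 28 days of screening, 5 of treatment and 30 of follow-up: 28 / (28 + 5 + 30) = 28 / 63 = 44% of planned participation at most. This is calendar time before any drug exposure, not a share of events or data.

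**The case against.** The strongest case on the other side has three parts.

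First, the general definition in 8.1.1.1 speaks of a subject who has been given a medicinal product, so keeping pre-dose events off the AE page may look like a consistent choice. This does not hold, because the same section goes on to name pre-dose procedure complications as AEs.

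Second, 8.1.3.1 says the biopsy follows the site's standard of care, and 4.2 says patients need no additional study-specific invasive procedures. The biopsy might therefore not count as protocol-mandated. But Table 1 schedules it, and 8.1.1.1 and 8.1.1.6 both give biopsy as an example of such a procedure.

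Third, the practical effect is one listing in about 12 patients, and only if the site follows one sentence against several others. This stands, and it sets the size of the point.

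A reader might also infer more than the documents support:

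- That worsening after dosing cannot be identified. It is still an AE and still treatment-emergent (step 5).
- That SAP 9.4 requires a graded pre-dose AE record. Its worsening limb fits more naturally with one, but the SAP does not state that requirement.
- That the redirected events are ungraded. The CRF is not among the documents, so what the Medical History page holds is unknown.
- That pre-dose serious events would go unreported to the sponsor. The 24-hour duty stands.
- That 44% of the safety data are at risk. The figure measures time only.

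**Conclusion.** The text is wrong as written: it is an internal inconsistency and a minor one. Protocol 8.1.1.2 conflicts with its own first sentence, with 8.1.1.1 and with Table 1, footnote 10, on where to record events between consent and first dose. The consequence is conditional. If the site follows the Medical History sentence, pre-dose biopsy complications and serious events lack an AE-page record and an assured grade and procedure-causality assessment, and they drop out of the listing of all AEs. The treatment-emergent tables and the laboratory grading are not changed by events confined to the pre-dose period.

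Two assumptions matter. One is that the Medical History page does not itself collect grade and relation to procedure; if it does, the loss shrinks to the place of listing. The other is that a worsening is entered as a new AE with its own onset date, as 8.1.1.1 implies. The documents give no expected number of pre-dose events, so the number affected cannot be stated.

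**What to change.** Reconcile the passages on one rule. Delete the Medical History sentence in Protocol 8.1.1.2 and apply the consent-based rule already in 8.1.1.1. Events with onset after consent then go on the AE page with grade, seriousness and relation to procedure, flagged as pre-treatment. If the sponsor prefers to keep the sentence, it should at least exempt procedure complications and SAEs.

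Protocol 8.1.3.7 sends significant laboratory abnormalities noted during screening to medical history. It needs only a clarification: those with onset before consent and unrelated to a protocol procedure stay there. Moving every screening abnormality to the AE page would go too far, because some will have begun before consent.

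The cost is a wording change in the protocol and the CRF instructions, and a few more AE entries in about 12 patients. No visit, sample or planned AE table changes.
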